### **Data collection tool/instrument**

Data will be collected through adopted and adapted self-administered, structured questionnaires from 6,7, and 8-grade school-going adolescents at baseline and the end line. The questionnaire will be categorized into four main groups to assess the respondent's demographic data and their knowledge, attitude, and practices (KAP) about nutrition and WASH. Group A (demographic characteristic), group B contains physical assessment, group C included 24 Questions on KAP on nutrition that are adopted from the KAP manual developed by the Food and Agriculture Organization of the United Nations (2014) and group D are based on the 16 WASH items adopted from GSHS version 2013. The questionnaire will be translated into the Urdu language. Observation of the eating practices, school canteen, WASH, and school environment will be assessed through a checklist at baseline and end line.

### **Activities of baseline assessment**

Activities	Purpose	Frequency
KAP survey	To know the KAP regarding nutrition and WASH	Baseline and end line
Anthropometric measurements	To identify the number of thin, underweight, Overweight, and Obese adolescents in 6-8 grade	Baseline and end line
Physical assessment	To identify the health status of adolescents	Baseline and end line

Monitoring CBC, Zinc, Calcium, and Vitamin D level	To identify the deficiency of micronutrients at baseline and improvement at the end line	Baseline & end line
Observations	To assess the practices related to major determinants of malnutrition i.e. nutrition, water, sanitation, and hygiene.	Baseline & end line

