**b. Dependent variables/Outcome of study**

1. Body Mass Index: All school going 6- 8 grade adolescents will undergo anthropometric measurements such as height, and weight (BMI). The measurement will be taken at baseline and end line by using WHO standard growth chart.
2. Micronutrients: Blood sample will be collected twice (baseline and end line) from a subset of 108 adolescents (54 intervention group,54 control group). The blood samples will help to assess the impact of intervention on micronutrient deficiencies (Iron, Zinc, Calcium, CBC, Vitamin D)
3. Physical examination: Physical examination like hair, skin, nail, eye (bitot spot), mouth (dental caries), and goiter will be assessed for micronutrient deficiencies at baseline and end line.
4. Knowledge, attitude, and practices regarding nutrition and WASH: a structured questionnaire will be used to collect data on nutrition and WASH-related indicators. The survey will be administered at baseline and end line. The indicator assessed will be adolescent health status and knowledge, attitude, and practices regarding nutrition and WASH practices.

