### **Secondary objective**

To measure the impact of school-based nutrition education and water, sanitation, and hygiene intervention on micronutrient levels among early adolescents.

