**Post-intervention phase (Duration 2 months)**

End line Assessment	KAP survey	Early school adolescents (6,7,8 grade)	Researcher	KAP survey questionnaire
	Anthropometric measurement (BMI)	Early school adolescents (6,7,8 grade)	Researcher	
 
• Height scale
 
• Weight machine
 
• WHO growth chart
 

	Micronutrient assessment (Blood complete picture, Zinc and Calcium)	30 % of the total Adolescents sample (108 participants, 54 from each group)	LAB (Aga Khan Lab)	Blood test from Lab
	Physical assessment (skin, hair, eyes, nail, tongue, teeth, gums,)	Early school adolescents (6,7,8 grade)	Researcher	Checklist
	Observation (Eating and WASH practices) at School	Early school adolescents (6,7,8 grade)	Researcher	Observation Checklist
Dissemination Phase				
	Research uptake	Stakeholders (adolescents, mother/immediate caretakers, school teachers, school management. community stakeholder	Research team	Health mela, health screening, publication

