### **Sample Size & Sampling Strategy**

The sample size was calculated by using PASS software. Sample sizes were estimated to change in nutritional status of early adolescent boys and girls. A sample size of 360 adolescents

(180 in each intervention and control group) will achieve 80% power assuming 42% malnutrition among students in the control arm and at least 6% reduction in the intervention arm having 90 students from each school at a two-sided 5% level of significance.

To assess the micronutrient levels (Iron, Zinc, Calcium, CBC, and Vitamin D) through a blood sample, a subset of 108 adolescents 6-8 grade school going adolescents (54 intervention group, 54 control group) from this total sample size (360) will be selected through random selection.

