### Data analysis plan

Quantitative variables will be described by means and standard deviations whereas median with interquartile range will be mentioned for qualitative variables. Frequencies and percentages will be calculated for the knowledge, attitude, and practices of adolescents regarding nutrition and WASH. The comparison between intervention and control at baseline and end line will be performed by using paired t-test and Chi-square. For the variables that are not normally distributed, a nonparametric test McNamara will be used. Binary logistic regression and multiple linear regression will be used to assess the effect of intervention. All the statistical analyses will be conducted using SPSS version 23. A p-value less than 0.05 will be considered statistically significant.

Descriptive	Inferential

 
• Mean, SD Normally distributed
 
• Median, interquartile range Skewed distribution
 
• Percentages and frequencies of knowledge, attitude, and practices
 
	
 
• Chi-Square-McNamara knowledge, attitude, and practices
 
• T- test paired Continuous variables
 
• Binary logistic regression and multiple linear regression
 
• Proportion changes - chi-square Observational checklist
 

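### The blood endpoint is worded three ways, and the test named for continuous variables is a paired t-test, which does not compare the arms

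*Protocol*

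**What the plan says.** The protocol words the blood endpoint in three ways.

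- **Levels.** The Secondary objective is the impact of the "intervention on micronutrient levels among early adolescents". Sample Size & Sampling Strategy (RCT phase) repeats this: "To assess the micronutrient levels (Iron, Zinc, Calcium, CBC, and Vitamin D) through a blood sample".
- **Deficiencies.** Under Dependent variables/Outcome of study: "The blood samples will help to assess the impact of intervention on micronutrient deficiencies". No cut-off is given.
- **Deficiency, then improvement.** In the table Activities of baseline assessment, the purpose of the blood tests is "To identify the deficiency of micronutrients at baseline and improvement at the end line". How improvement is measured, and in whom, is not stated.

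The subset is a random draw: "54 intervention group, 54 control group) from this total sample size (360) will be selected through random selection". The post-intervention table describes it as "30 % of the total Adolescents sample (108 participants, 54 from each group". No power, effect size or SD is given for it.

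The Data analysis plan (RCT phase) says: "The comparison between intervention and control at baseline and end line will be performed by using paired t-test and Chi-square". Its table gives the paired t-test to continuous variables and chi-square/McNemar to the knowledge, attitude and practice items. Logistic and linear regression are named for the effect of the intervention, but neither is tied to the blood outcome.

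**The concern.** A level is a continuous value available for every sampled pupil. Deficiency is a yes/no status. Improvement from deficiency may be either, and may be read as applying only to some pupils. The three lead to different tests and differ in what 54 per arm can detect. Nothing ranks them, so the choice could be made after the results are known, separately for each marker.

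The analysis section adds a second problem. A paired t-test compares each pupil's two values. Run in the intervention arm, it tests whether levels changed over the study period and not whether they changed more than in controls. The secondary objective concerns the impact of the intervention, so it needs the contrast between arms. At stake is a real effect missed through a weak endpoint, or a within-arm change reported as an intervention effect.

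**Working it through.** **Inputs from the protocol.** The subset is 0.30 × 360 = 108, or 54 per arm; this reproduces. The test is "at a two-sided 5% level of significance", stated for the main sample and applied here to the subset. The Introduction gives 180 for the subset, a separate inconsistency; 108 is used here because the other sections agree on it.

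**Assumed, because the protocol gives no figure.** Normal levels with equal SD, no dropout, clustering ignored at first, deficiency prevalence 20-60%, and baseline to end-line correlation r of 0.5-0.8.

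**1. Levels, unadjusted.** The noncentral t with n = 54 per arm gives 80% power at d = 0.544 SD. The normal approximation agrees: (1.960 + 0.842) × √(2/54) = 0.539. This d is chosen as a reference; it is not a planned effect.

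**2. The same shift scored as deficient yes/no.** If a proportion p1 of controls is deficient, a shift d leaves p2 = Φ(Φ⁻¹(p1) − d) in the intervention arm. With p̄ = (p1 + p2)/2,

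power = Φ{ [ |p1 − p2|√n − 1.96√(2p̄(1 − p̄)) ] / √( p1(1 − p1) + p2(1 − p2) ) }.

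Example at p1 = 0.40: p2 = Φ(−0.253 − 0.544) = 0.213 and p̄ = 0.306. The numerator is 0.187 × 7.348 − 1.96 × 0.652 = 0.10 and the denominator is 0.638. Power is Φ(0.16) = 56%.

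| Control prevalence | Power, deficient yes/no | Per arm for 80% |
|---|---|---|
| 20% | 41% | 140 |
| 40% | 56% | 96 |
| 60% | 61% | 86 |

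The last column uses d = 0.54. At a smaller shift of 0.4 SD, levels have 55% power and deficiency 27-38%.

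**3. Levels adjusted for baseline.** The effective shift is d/√(1 − r²). At r = 0.5 it is 0.544/0.866 = 0.63, with about 90% power. At r = 0.7 it is 0.544/0.714 = 0.76, with about 98% power. Both blood samples are already planned.

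**4. A conditional check on improvement.** Suppose it were assessed only in pupils deficient at baseline, with no treatment effect and no true change. At 30% deficient that is 0.30 × 54 ≈ 16 pupils per arm. The cut-off is c = −0.524 SD and the expected gain is (1 − r)φ(c)/p = (1 − r) × 0.348/0.30, that is 0.58 SD at r = 0.5 and 0.23 SD at r = 0.8. Of these pupils, 48% (r = 0.5) to 30% (r = 0.8) would no longer be deficient. In simulation, a paired t-test within one arm is significant in about 67% of such trials at r = 0.5 and 30% at r = 0.8. A between-arm test in the same pupils stays near 5%. Mean change over all sampled pupils has no regression to the mean, because they are drawn at random and not for low values.

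**5. Clustering.** With two schools per arm and 27 sampled pupils per school, an assumed ICC of 0.05 gives a design effect of 1 + 26 × 0.05 = 2.3, or 54/2.3 = 23.5 effective pupils per arm. Power at d = 0.54 falls to 46% for levels and 28% for deficiency (40% prevalence). Levels still do better, but every figure in steps 1 to 3 is optimistic.

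**The case against.** The text on improvement is a purpose entry in an activities table, and the activity in its row is monitoring of levels. It defines no endpoint and does not confine scoring to pupils deficient at baseline. A reader might infer that the trial would report improvement even if the intervention did nothing. The protocol does not support that: the subset is random, controls are bled on the same schedule, and regression to the mean acts on both arms alike. This part of the objection stands, and the artefact remains only a conditional, within-arm caution.

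A reader might also infer that the same data could yield opposite conclusions under the different wordings. The calculations show a greater chance of missing an effect, not of reversing one.

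It can further be said that two sections say levels, that deficiency prevalence is a legitimate public-health outcome, that detail may sit in a statistical analysis plan not shown here, and that linear regression is already named. Each is fair. But the outcome section itself says deficiencies, so an analysis plan choosing levels would depart from it. The protocol's own table gives continuous variables a paired t-test and leaves the regression unassigned. Finally, the power loss has no stated baseline, since the protocol claims none for the subset. That limits the figures to relative ones.

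**Conclusion.** The point holds. One blood endpoint has three wordings, and the test assigned to continuous variables does not compare arms. Relative to 80% power on unadjusted levels at 0.54 SD, scoring deficiency yes/no costs roughly 19 to 39 percentage points (61% to 41%), and adjusting for baseline gains about 10 to 18. These sizes rest on normal levels, the assumed prevalence and correlation ranges, and no clustering. They are not losses from a power that the protocol promised.

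The false-gain risk, about 30-67% of null trials at 30% deficiency and r of 0.8 down to 0.5, applies only to a paired test within one arm restricted to baseline-deficient pupils. The protocol does not specify that analysis; its wording on improvement and its choice of paired tests leave it open.

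**What to change.** Use one definition in the Secondary objective, Dependent variables/Outcome of study, Activities of baseline assessment and the Data analysis plan: the end-line level of each listed marker in all sampled pupils (54 per arm). List the markers once, since iron appears in the outcome and sampling sections but not in the activities table.

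In the Data analysis plan, replace the paired t-test for this endpoint with a between-arm linear regression that has the pupil's baseline level as covariate and accounts for school. With two schools per arm, accounting for school will lower precision, and the protocol should say so.

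Report end-line deficiency prevalence by arm as supportive, with cut-offs stated in advance. Report any change among baseline-deficient pupils descriptively only, side by side for both arms.

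The cost is wording in four places, with no extra visits or blood draws. The small downside is that the headline becomes a mean difference and not a deficiency rate.

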### **Validity and reliability**

#### **Quantitative tool**

Standardization of the questionnaire will be ensured by carrying out a pilot testing on 10 % of 6-8 grade school-going adolescents in a public school from the same urban area (Gojra). Amendments to the tool will be made based on the pilot testing. Adolescents' KAP part will be assessed by questions based on the dietary part of the validated English version of the Food Agriculture Organization (FAO). KAP survey on WASH will be assessed by questions based on the Water, Sanitation, and Hygiene component of the Global School Health Survey (Survey Questionnaire will be translated into the Urdu language).

#### **Data collection process**

The principal investigator will collect data. Initially, a meeting with the school principal and teachers will be done to share the overall scope and objectives of the study and to seek their cooperation throughout the study. Secondly, to approach 6, 7, and 8-grade adolescents, informed consent will be first taken from their mothers/immediate caretakers and school management. Before collecting the data, a written informed assent will also be taken from the participants available in Urdu and English or the local language. Study participants will be briefed about the purpose of the study and assured about anonymity and confidentiality of the information shared. Finally, the survey questionnaire will be completed which will take around 25-30 minutes. In case, participants have any queries related to the questionnaire, an explanation will be provided

to them. Physical assessment will be done by the principal investigator which will take almost 10 minutes/ individual. For the biochemical markers assistance from the local Aga Khan Laboratory will be sought phlebotomists /lab assistants from the Aga Khan laboratory will go to the concerned educational institute and draw blood samples from the participants who have given their consent for the test.

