## **Philosophical underpinning**

The study will be guided by the post-positivist paradigm. This paradigm has tended to provide the worldview for most research conducted on human behavior typical of the education context (Kivunja, 2017). Research in this mode requires an ability to see the whole picture, to take a distanced view or an overview. This paradigm allows for observation without experimentation and formulation of hypotheses to be tested.

For clarity purposes, this study will be divided into three phases. Phase I is the formative phase for the development of the intervention module. Phase II is the RCT phase in which the baseline assessment and intervention module will be implemented through the teachers and researcher along with the end-line assessment. Phase III will be research uptake. According to Guba (1990) in post-positivism, reality can never be fully understood but at best only approximated. Data, evidence, and rational considerations shape knowledge. The researcher will collect information on instruments based on measures completed by the participants or by observations recorded by the researcher. Being objective is an essential aspect of competent inquiry; the researcher will examine methods and conclusions for bias like the standard of reliability and validity.

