**Outcome of the study**

The main outcome is the reduction of malnutrition among school going early adolescents (6 to 8 grade) in a school setting that will be assessed through;

1. Body Mass Index
2. Micronutrients
3. Physical examination
4. Knowledge, attitude, and practices regarding nutrition and WASH

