**Detail of project activities**

Outline of the study
Formative Phase

Activities	Strategies	Target Population	Channels	Material
Formative assessment qualitative	Focus group discussions (FGDs)	
 
• Adolescents (6,7,8 grade)
 
• Teachers
 
• Mothers/immediate caretakers
 
	Researcher	FGD interview guide
	Key informant interview (KII)	School management	Researcher	Interview guide
	School document analysis	
 
• Curriculum of 6,7,8 grade
 
• School policy
 
	Researcher with teachers	Reviewing school curriculum, textbooks, and policy
RCT Phase				
Baseline assessment	Knowledge, attitude, and practices (KAP) assessment	Early school adolescents (6,7,8 grade)	Researcher	KAP survey questionnaire
	Anthropometric measurement (BMI)	Early school adolescents (6,7,8 grade)	Researcher	-Height scale -weight machine -WHO growth chart
	Micronutrient assessment (complete blood picture, Zinc and serum calcium, Vitamin D)	Adolescents sample (subset of 108 participants, 54 from each group)	LAB (AKU)	A blood test from Lab
	Physical assessment (skin, hair, eyes, nail, tongue, teeth, gums,)	Early school adolescents (6,7,8 grade)	Researcher	Check list
	Observation (Eating and WASH practices) at school	Early school adolescents (6,7,8 grade)	Researcher	Observation checklist
Intervention phase (Duration 4 months)				

Module development	Development of module on Nutrition and WASH component	For early adolescents (6,7,8 grade)	
 
• Research team
 
• Nutritionist
 
	
 
• Pakistan Dietary guideline
 
• WHO guidelines
 
• UNICEF guidelines
 
• Literature search
 

Workshop	2 workshops will be conducted for the school teachers	For School teachers (Teaching 6,7,8 grade)	Researcher	Based on the Module & teaching strategies
Deworming	Administering Deworming medicine to study participants	Early adolescents (6,7,8 grade)	School teachers	Tab Zentel
	Micronutrient supplementation to study participants	Early adolescents (6,7,8 grade)	School teachers	Micronutrient supplementation 1 tab daily for three months

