##### ***Baseline assessment***

Knowledge, attitude, and practices regarding nutrition and WASH will be assessed among school adolescents through a KAP survey along with anthropometric

measurement, physical assessment, and micronutrient assessment (CBC, Zinc, Calcium,).

The observation on the eating and WASH practices of grade 6-8 adolescents will be done by the researcher during break time (lunch time) and school off timings.

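### The role that trains the intervention teachers also scores physical signs and observed eating and WASH practices in both arms, knowing the arm, yet these results are used as evidence of effect

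*Protocol*

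**What the plan says.** **Who assesses.** Under Phase II, Data collection process, the Protocol says "The principal investigator will collect data" and "Physical assessment will be done by the principal investigator". Laboratory staff draw the blood. The tables under Detail of project activities and Post-intervention phase enter *Researcher* as the channel for the physical assessment and for the eating and WASH observation, at both time points. The Baseline assessment section agrees: "The observation on the eating and WASH practices of grade 6-8 adolescents will be done by the researcher during break time".

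**Who prepares and gives the intervention.** In the intervention part of the activity table, "2 workshops will be conducted for the school teachers", again with *Researcher* as the channel. Weekly sessions, deworming and supplements are assigned to school teachers.

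**What the assessments are used for.** Outcome of the study opens with "The main outcome is the reduction of malnutrition among school going early adolescents" and lists physical examination among the four means of assessing it. The dependent-variables section adds: "Physical examination like hair, skin, nail, eye (bitot spot), mouth (dental caries), and goiter will be assessed for micronutrient deficiencies at baseline and end line". The Post-intervention phase section uses the physical assessment to judge whether the intervention worked and the checklist to evaluate change. The Phase II Data analysis plan tests the checklist by chi-square.

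**Allocation.** Study Setting assigns four whole schools, two to each arm.

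**The concern.** Hair, skin, nail, tongue and gum signs, and eating or handwashing watched at break time, depend on the scorer's judgement. If the scorer knows the arm and has trained the teachers on one side of the comparison, expectation can lower the number of signs recorded, or raise the number of good practices recorded, in intervention schools only. Randomisation does not protect against this, because the error enters after allocation and differs by arm. A difference produced by the assessor could then be reported as reduced malnutrition or improved practice, alongside measured BMI and laboratory results that do not share the weakness.

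**Working it through.** The plan states no figure on this point, so the check sets the role assignments side by side.

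**Step 1: is it the same role?**

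| Task | Assigned to | Section of the Protocol |
|---|---|---|
| Physical assessment | Principal investigator | Data collection process (Phase II) |
| Physical assessment, baseline and end line | Researcher | Detail of project activities; Post-intervention phase |
| Eating and WASH observation | Researcher | The same tables; Baseline assessment |
| Teacher workshops | Researcher | Detail of project activities |
| Sessions, deworming, supplements | School teachers | Detail of project activities |

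The physical assessment is given to the principal investigator in one place and to the researcher in another, so the two terms denote one role for that task. For the observation, identity with the principal investigator is an inference from the general data-collection statement. The overlap with the workshops needs no inference, since both carry the label *Researcher*.

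**Step 2: does the assessor know the arm?** Yes. Each school belongs wholly to one arm, the assessment takes place at school, and the assessor ran the workshops. No masked assessor, independent assessor or second rater is named. The quantitative validity section covers only the questionnaire.

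**Step 3: do the exposed measures carry weight?** Physical examination does: it is a listed measure of the main outcome and a dependent variable. The checklist appears in neither list, but it is tested inferentially and used to evaluate change.

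**Step 4: what can be said about size?** Only an illustration on assumed values is possible. Assume no true effect, 180 pupils per arm (the Protocol's figure), no false positives, and independence between pupils (clustering ignored). Recorded prevalence is true prevalence × sensitivity. Take sensitivity 0.90 in control schools and a lower value in intervention schools. The chance of a two-sided p < 0.05 in the intervention's favour is

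Φ[(d − 1.96·SE₀) / SE₁],

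where d is the recorded difference, SE₀ the pooled and SE₁ the unpooled standard error.

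Example: true prevalence 40%, sensitivity 0.90 against 0.60.
- Recorded 0.40 × 0.90 = 36% and 0.40 × 0.60 = 24%, so d = 0.12.
- SE₀ = √(2 × 0.30 × 0.70 / 180) = 0.0483.
- SE₁ = √((0.36 × 0.64 + 0.24 × 0.76) / 180) = 0.0479.
- Φ[(0.12 − 0.0947) / 0.0479] = Φ(0.53) ≈ 70%.

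| True prevalence (assumed) | 0.90 vs 0.80 | 0.90 vs 0.70 | 0.90 vs 0.60 |
|---|---|---|---|
| 20% | 7% | 18% | 36% |
| 40% | 12% | 37% | 70% |
| 60% | 21% | 63% | 93% |

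The nominal chance in that direction is 2.5%. The table shows that the mechanism can produce a significant result. Its spread, 7% to 93%, also shows that no particular size can be asserted.

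**The case against.** **Teachers deliver the intervention.** This stands. A reader might infer that the researcher teaches the pupils, so that pupils perform for the person they associate with the lessons. The phrase "intervention module will be implemented through the teachers and researcher along with the end-line assessment" invites that reading, but its sentence also has the baseline assessment as a subject, so it can be read as a division of labour: teachers deliver and the researcher assesses. The activity tables assign every pupil session to teachers. What remains is that the assessor trained those teachers.

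**The researcher may not be the principal investigator.** For the observation this is possible, since the Protocol also mentions a research team. It does not remove the overlap, because workshops and observation carry the same label.

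**The checklist is not part of the main outcome.** Correct. The fourth listed measure is knowledge, attitude and practices, taken by a self-administered questionnaire. The concern about the checklist rests on the analysis plan and the post-intervention section.

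**Nothing says the measures weigh equally, and a SAP could rank them.** Fair. The expected gain in nutritional status is stated as BMI, and physical signs are tied to micronutrient deficiency and health status. But who assesses, and which measures define the main outcome, are fixed in this document, which attaches no caution to the physical signs.

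**Some signs are less subjective, and unmasked school trials are common.** Dental caries, goitre and Bitot spots leave less room for judgement, and a structured checklist helps. Pupils and teachers cannot be masked here. Assessment could still be separated from teacher training, and the results could be labelled for what they are. The Protocol offers only a general remark about objectivity.

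**Conclusion.** The point holds in a limited form. The role that trains the intervention teachers also scores physical signs and observed practices in both arms, with the arm known, and the Protocol uses these results to judge effectiveness without qualification. Arm-dependent scoring could therefore appear as an effect.

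The size cannot be estimated, because the Protocol gives no prevalence of signs and no rater-error figure. A reader might assume a prevalence and a degree of under-calling and set the resulting false difference against the 6% reduction used for the sample size. The document does not support that comparison: the inputs would be invented, and the 6% refers to the prevalence of malnutrition, not to having a physical sign.

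Height, weight and laboratory values are much less exposed, so the concern does not extend to the BMI or micronutrient results. The change is worth making because it is cheap and prevents a claim that the data could not support. It does not call the whole design into question.

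**What to change.** 1. In Outcome of the study, the dependent-variables section and the Post-intervention phase section, state that physical signs are supportive and descriptive because the assessor is unmasked and trains the intervention teachers.
2. In the Phase II Data analysis plan and the Post-intervention phase section, state the same for the observation checklist.
3. Rest the claim of reduced malnutrition on measured height and weight (BMI), and the micronutrient claim on laboratory values.
4. If an existing research-team member took no part in the workshops or sessions, assign the end-line physical assessment and observation to that person. The Protocol does not show that such a person exists, so items 1 to 3 should not depend on it. This person would still see which school they are in. The gain is separation from the training, not masking.

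The cost is Protocol wording and, where feasible, one reassignment. The drawback is that physical signs and observations can no longer be claimed as proof of efficacy.
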